**9.2.3. Serious Adverse Events**

**Serious Adverse Event (SAE):**

An AE or suspected adverse reaction is considered “serious” if, in the view of either the site principal investigator or sponsor, it results in any of the following outcomes:

- Death,
- A life-threatening AE\*,
- Inpatient hospitalization or prolongation of existing hospitalization,
- A persistent or significant incapacity or substantial disruption of the ability to conduct normal life functions, or
- A congenital anomaly/birth defect.
- Important medical events that may not result in death, be life-threatening, or require hospitalizations may be considered serious when, based upon appropriate medical judgment they may jeopardize the patient or subject and may require medical or surgical intervention to prevent one of the outcomes listed in this definition. Examples of such medical events include allergic bronchospasm requiring intensive treatment in an emergency room or at home, blood dyscrasias or convulsions that do not result in inpatient hospitalization, or the development of drug dependency or drug abuse.

\* Life-threatening AE. An AE is considered “life-threatening” if, in the view of either the site principal investigator or sponsor, its occurrence places the patient or subject at immediate risk of death. It does not include an AE that, had it occurred in a more severe form, might have caused death.

SAEs will be:

- Assessed for severity and relationship to study product and alternate etiology.
- Recorded on the appropriate SAE data collection form and eCRF.
- Followed through resolution.
- Reviewed and evaluated by an Independent Safety Monitor (ISM) (as deemed necessary), the SMC (periodic review unless related), DMID, and the IRB.

At any time after protocol follow up period or completion of this study, if the site principal investigator or appropriate sub-investigator becomes aware of an SAE that is suspected to be

related to study product, the site principal investigator or appropriate sub-investigator will report the event to the DMID Pharmacovigilance Group.

#### 9.2.4. Adverse Events of Special Interest (AESI)

- Medically significant wheezing: defined as wheezing on physical exam sign of respiratory distress (tachypnea, retractions, or dyspnea), hypoxemia (O2 saturation < 95%), or new bronchodilator prescription, or use of daily bronchodilator therapy (not on an “as needed” basis) from receipt of the first vaccination through 3 months after the first vaccination. Will record presence or absence of any wheezing after V02 and whether wheezing is diffuse or localized, respiratory rate, oxygen saturation, medications associated with wheezing, and physician’s description on auscultation.
- Otitis Media and Wheezing at V02 only will be graded as follows:

Systemic (Quantitative)	Mild (Grade 1)	Moderate (Grade 2)	Severe (Grade 3)
Otitis Media	No interference with daily activity	Some interference with daily activity	Significant interference, prevents daily activity
Wheezing	No interference with daily activity	Some interference with daily activity	Significant interference, prevents daily activity

#### 9.2.5. Clinical Safety Laboratory Adverse Event Grading

*Note: Ranges have been modified to reflect local laboratory normal ranges for the site conducting this study*

Hematology	Mild (Grade 1)	Moderate (Grade 2)	Severe (Grade 3)
WBC cells/mm  ; 10  cells/μL (Decrease)	2.0 – 2.4	1.50 – 1.0	<1.5
HgB g/dL 9-12 years of age	9.5-10.4	8.5-9.4	<8.5

HgB g/dL Males $\geq$ 13 years of age	10.0 – 10.9	9.0 - < 10.0	< 9.0
HgB g/dL Females $\geq$ 13 years of age	9.5 – 10.4	8.5 - < 9.5	< 8.5
Platelets cell/mm  /UL	100- < 125	50- < 100	< 50
PT	1.1 - <1.25 x ULN	1.25 - < 1.50 x ULN	$\geq$ 1.50 x ULN
aPTT	1.1 - < 1.66 x ULN	1.66 - <2.33 x ULN	$\geq$ 2.33 x ULN

Chemistry	Mild (Grade 1)	Moderate (Grade 2)	Severe (Grade 3)
ALT	1.25 – < 2.5 x ULN	$\geq$ 2.5 – <5.0 x ULN	$\geq$ 5.0 x ULN
AST	1.25 – < 2.5 x ULN	$\geq$ 2.5 – <5.0 x ULN	$\geq$ 5.0 x ULN
Creatinine mg/dL	1.1 – 1.3 x ULN	>1.3 – 1.8 OR Increase to 1.3 to < 1.5 x subject's baseline	>1.8 x ULN OR Increase to $\geq$ 1.5 x subject's baseline

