## 9. ASSESSMENT OF SAFETY

### 9.1 Specification of Safety Parameters

Safety will be assessed by the frequency and severity of:

1. SAEs occurring from the time of the first study vaccination through 12 months after the first vaccination.
2. AESIs (wheezing, otitis media) and NOCMCs occurring from the time of the first study vaccination through 3 months after the first vaccination.
3. Solicited Adverse Events – reactogenicity events occurring from the time of experimental (first) study vaccination through 7 days after the first study vaccination. See tables listed in [section 9.2.2 and 9.2.6](#) for local upper respiratory, respiratory tract assessment, and systemic symptoms:
4. Unsolicited Non-Serious Adverse Events –non-serious AEs occurring from the time of the first study vaccination through approximately 21 days after the first study vaccination.
5. Clinical safety laboratory AEs occurring at approximately 7 days after the first vaccination. Parameters to be evaluated include a WBC, HGB, Platelet Count, ALT, AST, Serum Creatinine, Ferritin level, PT and aPTT. HGB will also be repeated at Day 22 if there is a drop in HGB level from screen to Day 8 of  $\geq 0.5$  g/dL or results are  $<$  lower limits of normal. If unable to collect at Day 22, collect at Day 57. If drawn at Day 22 and the results are still low, repeat at Day 57. If HGB results are still low at Day 57, no further PBMC collection will be done. HGB and Ferritin level will be drawn at Day 113. If the ferritin is  $< 15$  ng/mL and/or the HGB is less than the lower limits of normal, will recommend follow-up with primary care provider for consideration of multivitamins with iron.

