#### **9.5. Halting Rules**

Further enrollment and study vaccinations will be halted for SMC review/recommendation if any of the following are reported following experimental (first) vaccination:

- Any subject experiences laryngospasm, bronchospasm, or anaphylaxis within 1 day after administration of study product that is considered related to study product.
- Two or more subjects experience the same grade 3 Adverse Event of any kind after administration of study product through day 8 that is considered related to study product
- Two or more subjects experience generalized urticaria (defined as occurring at more than two body parts) within 3 days after administration of study product that is considered related to study product.

- Any subject experiences a study vaccine-related SAE from the time of the first study vaccination through the subject's last study visit.

Grading scales for solicited upper respiratory and systemic (subjective and quantitative) reactions are included in [Section 9.2.2](#).

If any of the halting rules are met following any subject receipt of the first study vaccination, then this trial will not continue with the remaining enrollments or study vaccinations without a review by and recommendation from the SMC to proceed.

DMID retains the authority to suspend additional enrollment and study interventions/ administration of study product during the entire trial, as applicable.

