3.3. Study Definitions and Derived Variables

Medically significant wheezing is defined as wheezing on physical exam, signs of respiratory distress (tachypnea, retractions, or dyspnea), hypoxemia (O_2 saturation < 95%), or new bronchodilator prescription, or use of daily bronchodilator therapy (not on an “as needed “basis) from receipt of the first vaccination through 3 months after the first vaccination. Wheezing experienced after first vaccination through Visit 02 is considered a solicited event. Wheezing recorded after Visit 02 is considered an AESI. For all wheezing events the following will be recorded: whether wheezing is diffuse or localized, respiratory rate, oxygen saturation, medications associated with wheezing, and physician’s description on auscultation.

For laboratory and immunogenicity measures the baseline value will be defined as the last value obtained prior to the first vaccination/dose of study product.

Individual Hemagglutination inhibition (HAI) and neutralization results will be reported as a titer with values of 10×2^k , where $k=0, 1, 2$, etc. The lower limit of detection for the HAI and neutralization assays is 1:10; values below the limit of detection will be reported as ‘<10’. Values used in analysis will be imputed as one-half the limit of detection ($10/2 = 5$). For analysis, the geometric mean of repeated HAI or neutralization results will for each subject and visit will be computed and used as the response for all subsequent calculations.

Individual nasal sIgA results will be reported as a titer with values of 2^k where $k=0, 1, 2$, etc. The lower limit of detection for the nasal sIgA results is 2; values below the limit of detection will be reported as <2. Values used in analysis will be imputed as one-half the limit of detection ($2/2 = 1$). For analysis, the geometric mean of repeated sIgA results for each subject and visit will be computed and used as the response for all subsequent calculations. Relative (normalized) strain-specific sIgA results will be calculated by dividing the strain-specific value by total sIgA at each time point for each subject.

The lower limit of detection for the frequency of conserved internal viral protein-specific IFN- γ T cells per million peripheral blood mononuclear cells (PBMC) as measured by ELISPOT assay is 0.

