9.6. Clinical Laboratory Evaluations

Clinical laboratory parameters to be evaluated at the Screening Visit (Visit 00) and on Day 08 (Visit 02) will include a White Blood Cell Count (WC), HGB, HCT (only at Visit 00), Platelet Count, ALT, AST, Serum Creatinine, Ferritin (at Visit 00), Prothrombin Time (PT) and Activated Partial Thromboplastin Time (aPTT). The grading scales for clinical laboratory evaluations are presented in Table 11 and Table 10. Clinical laboratory evaluations assessed on Day 1 prior to the first study vaccination will be considered as baseline.

Subjects with HGB below the lower limit of normal (LLN) at Day 8, or subjects who experience a drop of ≥ 0.5 g/dL between screening and Day 8, will have HGB re-drawn at Day 22. If HGB remains low (result is less than LLN or ≥ 0.5 g/dL lower than screening levels) at Day 22, or if HGB is not collected at Day 22, hemoglobin labs will be re-drawn at Day 57. Any subject where HGB results remain low at Day 57 will have no further PBMC collected. HGB and Ferritin will be drawn for all subjects at Day 113 (approximately 22 days post QIV vaccination). Ferritin results taken at Day 57 will be used for clinical decision making only – values will not be graded or included in summaries of clinical laboratory data, but will be included in the listings of hematology results (Listing 15).

The distribution of laboratory results by severity, study day and treatment group will be presented beginning with [Table 54](#), and continuing through [Table 65](#). Descriptive statistics including mean, standard deviation, median, minimum and maximum values and change from baseline by study day will be summarized for each parameter in [Table 59](#) and [Table 67](#). Box plots illustrating the change from baseline for each laboratory parameter will be presented in [Figure 56](#), [Figure 57](#), [Figure 58](#), [Figure 59](#), [Figure 60](#), [Figure 61](#), [Figure 62](#), and [Figure 63](#). Subject visits with abnormal laboratory results, Grade 1 severity or higher, will be presented in [Table 52](#) and [Table 53](#) for chemistry and hematology parameters, respectively. Abnormal results will be summarized by visit and study arm in [Table 58](#) and [Table 66](#) for chemistry and hematology parameters, respectively.

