Table 11: Laboratory Adverse Event Grading Scale (Chemistry)

Chemistry Parameter	Mild (Grade 1)	Moderate (Grade 2)	Severe (Grade 3)
ALT	1.25 – < 2.5 x ULN	\geq 2.5 – <5.0 x ULN	\geq 5.0 x ULN
AST	1.25 – < 2.5 x ULN	\geq 2.5 – <5.0 x ULN	\geq 5.0 x ULN
Creatinine mg/dL	1.1 – 1.3 x ULN	>1.3 – 1.8 OR Increase to 1.3 to < 1.5 x subject's baseline	>1.8 x ULN OR Increase to \geq 1.5 x subject's baseline

14.1 Description of Study Subjects**14.1.1 Disposition of Subjects****Table 12: Subject Disposition by Treatment Group – All Enrolled Subjects***

Subject Disposition	M2SR (N=X)		Placebo (N=X)		All Subjects (N=X)	
	n	%	n	%	n	%
Screened	--	--	--	--	x	--
Enrolled/Randomized	x	100	x	100	x	100
Received First Vaccination	x	xx	x	xx	x	xx
Received Second Vaccination	x	xx	x	xx	x	xx
Received All Scheduled Vaccinations ^a	x	xx	x	xx	x	xx
Completed Final Blood Draw (Study Day 113)	x	xx	x	xx	x	xx
Completed Follow-up (Study Day 366) ^a	x	xx	x	xx	x	xx
Completed Per Protocol ^b						

Note: N=All Enrolled Subjects
^a Refer to Listing 16.2.1 for reasons subjects discontinued or terminated early.
^b Refer to Listing 16.2.3 for reasons subjects are excluded from the Analysis populations .

Table 13: Analysis Populations by Study Group – All Enrolled Subjects

Analysis Populations	Reason Subjects Excluded	M2SR (N=X)		Placebo (N=X)		All Subjects (N=X)	
		n	%	n	%	%	n
Safety Population	Did not receive first study vaccination.	x	xx	x	xx	x	xx
Modified Intent-to-Treat Population	Any Reason						
	Did not receive first study vaccination.						
	No Baseline Sample						
	No Post-Baseline Sample						
	No Baseline HAI Results Reported						
	No Post-Baseline HAI Results Reported						
Per Protocol Population (All Visits)	Any Reason						
	Did not receive first study vaccination.						
	No Baseline Sample						
	No Post-Baseline Sample						
	No Baseline HAI Results Reported						
	No Post-Baseline HAI Results Reported						
Per Protocol Population (Day 8)	Any Reason						
	Visit not conducted						
	Sample not collected						
	Result not reported						
	Receipt of live or inactivated vaccine						
	Receipt of immunosuppressive therapy						
	Visit Out of Window by >1 Day						
	Other reason						
Per Protocol Population (Day 22)	Any Reason						
	Sample not collected						
	Result not reported						
	Receipt of live or inactivated vaccine						
	Receipt of immunosuppressive therapy						
	Visit Out of Window by >1 Day						
Other reason							

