^b Any subject with either a drop of > 0.5 g/dL or results less than the lower limit of normal (based on age and gender) at Day 22 will have hemoglobin re-drawn at Day 57

Table 62: Laboratory Results by Parameter, Maximum Severity, Time Point, and Study Group – White Blood Cells, Safety Population

Time Point	Study Group	N	None		Mild / Grade 1		Moderate/ Grade 2		Severe/ Grade 3		Missing	
			n	%	n	%	n	%	n	%	n	%
Screening	M2SR	x	x	xx	x	xx	x	xx	x	xx	x	xx
	Placebo											
Day 8	M2SR											
	Placebo											
Max Severity Post Baseline	M2SR											
	Placebo											

Note: The “Max Post Baseline” rows indicate the maximum severity experienced by each subject at any time point post baseline, including unscheduled assessments.
N = Number of subjects in the Safety Population

Tables with similar format:

Table 63: Laboratory Results by Parameter, Maximum Severity, Time Point, and Study Group – Platelets, Safety Population

Table 64: Laboratory Results by Parameter, Maximum Severity, Time Point, and Study Group – Prothrombin Time, Safety Population

Table 65: Laboratory Results by Parameter, Maximum Severity, Time Point, and Study Group – Activated Partial Thromboplastin Time, Safety Population

Table 66: Abnormal Laboratory Results Related to Study Treatment by Parameter, Maximum Severity, Time Point, and Treatment Group – Any Hematology Parameter

Hematology Parameter	Time Point	Study Group	N	N*	Mild/ Grade 1		Moderate/ Grade 2		Severe/ Grade 3	
					n	%	n	%	n	%
Any Hematology Parameter	Day 8	M2SR	x	x	x	xx	x	xx	x	xx
		Placebo	x	x	x	xx	x	xx	x	xx
	Max Severity Post Baseline	M2SR	x	x	x	xx	x	xx	x	xx
		Placebo	x	x	x	xx	x	xx	x	xx
Hemoglobin	Day 8	M2SR	x	x	x	xx	x	xx	x	xx
		Placebo	x	x	x	xx	x	xx	x	xx
	Day 22 ^a	M2SR	x	x	x	xx	x	xx	x	xx
		Placebo	x	x	x	xx	x	xx	x	xx
	Day 57 ^b	M2SR	x	x	x	xx	x	xx	x	xx
		Placebo	x	x	x	xx	x	xx	x	xx
	Max Severity Post Baseline	M2SR	x	x	x	xx	x	xx	x	xx
		Placebo	x	x	x	xx	x	xx	x	xx
White Blood Cells	Day 8	M2SR	x	x	x	xx	x	xx	x	xx
		Placebo	x	x	x	xx	x	xx	x	xx
	Max Severity Post Baseline	M2SR	x	x	x	xx	x	xx	x	xx
		Placebo	x	x	x	xx	x	xx	x	xx
Platelets	Day 8	M2SR	x	x	x	xx	x	xx	x	xx
		Placebo	x	x	x	xx	x	xx	x	xx

Table 66: Abnormal Laboratory Results Related to Study Treatment by Parameter, Maximum Severity, Time Point, and Treatment Group – Any Hematology Parameter (Continued)

Hematology Parameter	Time Point	Study Group	N	N*	Mild/ Grade 1		Moderate/ Grade 2		Severe/ Grade 3	
					n	%	n	%	n	%

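### The WBC-decrease grading row is wrong in both documents: 1.0 to 1.49 is both Grade 2 and Grade 3, and values above 1.5 and below 2.0 have no grade

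*Protocol*

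**What the plan says.** Protocol 9.2.5 grades white-cell decrease, in 10^3 cells/µL, as "Decrease) 2.0 – 2.4 1.50 – 1.0 <1.5": 2.0 to 2.4 is Grade 1, the next range is Grade 2 (printed high to low), and anything below 1.5 is Grade 3. SAP Table 10 carries the same three entries.

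The grades are used in four places:

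- Protocol 9.1 lists five safety parameters, judged by frequency and severity. The fifth is "Clinical safety laboratory AEs occurring at approximately 7 days after the first vaccination", and WBC is in the Day 8 panel.
- SAP Table 62 is "Laboratory Results by Parameter, Maximum Severity, Time Point, and Study Group – White Blood Cells, Safety Population". Its columns are None, Grade 1, Grade 2, Grade 3 and Missing.
- SAP 9.6 sets the entry rule for the abnormal-result listings: "Subject visits with abnormal laboratory results, Grade 1 severity or higher, will be presented in" Tables 52 and 53.
- Protocol 9.5 halts enrolment and vaccination if "Two or more subjects experience the same grade 3 Adverse Event of any kind after administration of study product through day 8", provided the events are considered related.

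Two smaller slips concern the same laboratory data. The first limb of creatinine Grade 2 reads ">1.3 – 1.8 OR Increase to 1.3 to < 1.5 x" the child's baseline, with no multiple of ULN after 1.8, although the Grade 1 and Grade 3 cells state one (Protocol 9.2.5, SAP Table 11). SAP 9.6 also says "Clinical laboratory evaluations assessed on Day 1 prior to the first study vaccination will be considered as baseline".

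**The concern.** A severity scale should give each abnormal value exactly one grade, and the grade should rise as the value worsens. This row does neither. A child at 2.2 is Grade 1, a child at 1.8 is ungraded, and a child at 1.3 is Grade 2 or Grade 3 depending on which cell is read.

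For a value in the gap, the severity displays fail. It belongs in none of Table 62's columns and does not meet the Grade 1 entry rule for the listing. The any-haematology summary (Table 60) and, if the result is judged related, Table 66 would omit or misplace it too. A worse result can therefore disappear from displays that show a milder one.

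For a value in the overlap, the choice between moderate and severe is left open on a scale that feeds a paediatric halting rule.

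**Working it through.** **Inputs.** The three WBC entries in Protocol 9.2.5, identical in SAP Table 10. Taking the Grade 2 range as 1.0 to 1.5 inclusive:

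- Grade 1: 2.0 ≤ x ≤ 2.4
- Grade 2: 1.0 ≤ x ≤ 1.5
- Grade 3: x < 1.5

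**Overlap and gap.**

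- Grade 2 and Grade 3 together: 1.0 ≤ x < 1.5
- Below Grade 1 but in no grade: 1.5 < x < 2.0
- Grade 2 alone: x = 1.5

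**Counts.** Reporting precision is not stated, so both plausible cases are shown. Each row covers the values from 1.0 to just under 2.0: 10 values at one decimal, 100 at two.

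| Row used | One decimal: two grades / none / one | Two decimals: two grades / none / one |
|---|---|---|
| As printed | 5 / 4 / 1 | 50 / 49 / 1 |
| Grade 2 1.0–1.5, Grade 3 <1.0 | 0 / 4 / 6 | 0 / 49 / 51 |
| Grade 2 1.5–1.9, Grade 3 <1.5 | 0 / 0 / 10 | 0 / 9 / 91 |
| Grade 2 1.5 to <2.0, Grade 3 <1.5 | 0 / 0 / 10 | 0 / 0 / 100 |

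As printed, the double-graded values are 1.0–1.4 (or 1.00–1.49) and the ungraded values are 1.6–1.9 (or 1.51–1.99).

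The second row tests whether the error lies in the Grade 3 limit. Moving that limit to <1.0 removes the overlap but leaves the whole gap. The third row supposes that 1.0 was a slip for 1.9; it works at one decimal but leaves 1.91–1.99 (9 values) ungraded at two. The fourth row leaves no overlap and no gap at either precision. Under it, the values split 5 and 5 between Grades 2 and 3 at one decimal, and 50 and 50 at two.

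**Could this be a reading fault?** Unlikely: two separate documents carry the same entries. The neighbouring haemoglobin row for ages 9 to 12 runs 9.5–10.4, 8.5–9.4, <8.5, in order and without overlap. The protocol's note that ranges were adapted to the local laboratory explains shifted limits, not an overlap together with a gap.

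**The two smaller slips.** With the multiple of ULN restored, creatinine Grade 2 becomes >1.3 to 1.8 × ULN, which joins Grade 1 (1.1 to 1.3) and Grade 3 (>1.8) exactly. On baseline, Protocol 8.2.1 schedules the safety panel at screening and Day 8, and Appendix A shows none at the Day 1 visit. The Day 1 sentence therefore has no data behind it, whereas SAP 3.3 says "the baseline value will be defined as the last value obtained prior to the first vaccination/dose of study product", which is the screening value.

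**The case against.** Several points can be made for the plan as it stands.

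- **There may be a fallback.** Protocol 9.2.1 has a study physician grade events outside the protocol's scales on a general mild/moderate/severe scheme, and 9.2.7 requires abnormal values to be recorded and followed regardless. But WBC is inside the protocol's scales. The general scheme mainly grades effect on daily activities and need for treatment, so it would tend to put a symptom-free child at 1.8 no higher than mild. Section 9.2.7 assigns no grade.
- **The value is not lost.** Listing 15 keeps the raw result, Table 67 gives WBC mean, SD, median and range by arm with change from screening, and Figure 60 shows change from baseline. This stands, and it limits the harm, but it does not correct Table 62 or the abnormal-result listing.
- **The halting rule can still be read.** Any count below 1.5 meets the explicit Grade 3 limit. This largely stands. Values in the gap could not trigger the rule under the corrected row either, since they would be Grade 2. The rule also needs two subjects and a relatedness judgement, and the sponsor can suspend enrolment independently.
- **Laboratory severity is not a named primary or secondary outcome measure**, and WBC has one scheduled post-dose draw. True. The point concerns safety grading and affects no estimate, power or sample size.
- **Other rows are not perfect at two decimals.** The haemoglobin row for ages 9 to 12 would leave 9.41–9.49 ungraded. True, but that row is sound at the one-decimal precision in which it is written. The WBC row fails at either precision.

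**Conclusion.** The row is wrong as written in both documents, and nothing elsewhere in the plan repairs it. Half the range from 1.0 to 2.0 carries two grades, and almost all the rest carries none. The counts assume only that the printed limits are read literally.

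The practical size is unknown. Neither document gives an expected frequency of counts below 2.0, and among about 50 healthy children there may be none. The consequence is confined to severity grading and the displays built on it, with a secondary ambiguity for the halting rule that has a defensible reading. It should be corrected because a threshold used for safety grading is wrong and the repair costs almost nothing. That Grade 2 was meant to run from 1.5 to just under 2.0 is an inference from the neighbouring limits. The creatinine and baseline slips are editorial, and the conclusion does not depend on them.

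**What to change.** In Protocol 9.2.5 and SAP Table 10, set WBC Grade 2 to 1.5 to <2.0 and keep Grade 3 at <1.5, with the sponsor confirming the intent. State that a value meeting two grades takes the higher. The corrected WBC row no longer needs that rule, but creatinine does, because its ULN and baseline limbs can disagree: 1.2 × ULN with a rise to 1.4 × baseline meets Grades 1 and 2. Apply the corrected row to any Day 8 WBC below 2.0 already collected.

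As editorial corrections, add the ULN multiple to the first limb of creatinine Grade 2 in Protocol 9.2.5 and SAP Table 11, and change the laboratory baseline in SAP 9.6 to the last pre-dose (screening) value, in line with SAP 3.3.

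The cost is one cell in each of two tables, one added sentence, two wording corrections and a check of stored Day 8 results. No samples are needed. Any value above 1.5 and below 2.0 would gain a Grade 2 flag, and values from 1.0 to 1.49 would be Grade 3 only.
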